3.2. Study Endpoints

3.2.1. Safety and Tolerability Endpoints

The safety and tolerability endpoints of this study are:

- Incidence of TEAEs and serious adverse events (SAEs) overall and by intensity.
- Changes from baseline in:
 - Safety laboratory test results.
 - ECG findings.
 - Vital signs measurements.
 - Pulmonary evaluations (PFTs and pulse oximetry).
- Incidence and level of ADA titers and Jo-1 Ab levels.
- Exploratory characterization of immune response to ATYR1940.

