6.2. Patient Management

All patients must provide written informed consent or assent, as appropriate, based on local age of majority, before the performance of any study-related procedures. Patients who are determined to be eligible for the study will be enrolled into the study at the baseline visit (Week 1) and will receive IV infusions of ATYR1940 weekly. Patients will attend posttreatment follow-up visits 1, 4, and 12 weeks following completion of dosing. The 12-week follow-up visit is the End-of-Study (EOS) visit.

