8.5.10.4. Reporting Serious Adverse Events

SAEs will be collected and recorded throughout the study period, beginning with the signing of the ICF through the EOS visit, or after the end of the study if thought to be related to ATYR1940.

The Investigator must report all SAEs within 24 hours of discovery to:

[REDACTED]
Email: [REDACTED]
Telephone number: [REDACTED]

A completed SAE report is to be sent to the Medical Monitor's attention within 24 hours of discovering the event. The initial report should include at least the following information:

- Patient's ID number;
- Description and date of the event;
- Criterion for serious; and
- Preliminary assignment of causality to ATYR1940.

The Medical Monitor will contact the Investigator via telephone for follow-up information regarding the SAE, as appropriate.

The Investigator, or designated party, should notify the appropriate IRB/EC of SAEs occurring at the study center and other AE reports received from aTyr, in accordance with local procedures and statutes.

SAEs that are considered as possible or probably related to the investigational product, and as unexpected (i.e., SUSARs), will be reported to the concerned Competent Authorities (CAs) and IRBs/ECs by the Sponsor or Sponsor's designee as required by applicable local regulations. Per regulation, any fatal or life-threatening SUSAR will be reported to the CAs/IRBs/ECs within 7 calendar days, and additional information within an additional 8 calendar days. The Sponsor or Sponsor's designee is required to submit any other SUSAR to the CAs/IRBs/ECs within 15 calendar days of notification. The Sponsor or its designee is also responsible for notifying the investigational sites of all expedited SAEs. The Investigator must keep copies of all expedited SAE information including correspondence with the Sponsor on file.

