9.2.8. Safety Analysis

9.2.9. Safety and Immunogenicity Analyses

Safety evaluations will be based on the incidence, type, and intensity of AEs, and changes from baseline in safety laboratory tests, ECG findings, vital signs measurements, PFTs, and pulse oximetry. Immunogenicity will be assessed based on the incidence of infusion site reactions, ADA titers, changes in Jo-1 and ADA titers over time, as appropriate, as well as changes from baseline over time in immune-based laboratory tests, including, for example, tryptase, complement factors, and cytokines. Safety variables will be tabulated and presented for all patients who receive any amount of study drug and have follow-up safety data. Tabulations will be presented for safety data overall and separately for the parent and extension studies.

AEs will be coded using the current version of the Medical Dictionary for Regulatory Activities (MedDRA) for purposes of summarization. The overall incidence of AEs occurring during the study will be summarized by MedDRA system organ class and preferred term. The incidence of TEAEs also will be summarized by system organ class

and preferred term. For the purpose of analysis, a TEAE is defined as any AE that occurs after administration of the first dose of ATYR1940 through the 12-week posttreatment follow-up visit, or any event that is present at baseline, but worsens in intensity or is subsequently considered drug-related by the Investigator. Severe TEAEs, SAEs, and discontinuation rates of study therapy due to TEAEs also will be summarized.

Events that are considered related to treatment (possibly, likely, or definitely drug-related) will also be tabulated. A tabulation will also be provided that enumerates TEAEs by maximum severity. Deaths, SAEs, and TEAEs resulting in study discontinuation will be tabulated, if warranted by the data.

All AEs occurring on study will be listed in by-patient data listings.

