Potential planned or unplanned protocol deviations noted during clinical monitoring will be documented by category (i.e., inclusion criteria, exclusion criteria, study drug, safety assessment, lab/endpoint data, visit window, informed consent, prohibited co-medication, overdose/misuse, and other). All deviations will be reviewed, categorized, designated important or not important, and finalized prior to database lock according to the Protocol Deviation Guidance document. Important protocol deviations will be defined as those potentially impacting safety, immunogenicity, or PK/PD assessments.

Relationship to study treatment

AEs related to study treatment will be defined as those entered as possibly, likely, or definitely. None and unlikely will be considered not related to study treatment. If relationship is missing, then the AE will be considered as related to study treatment.

Study day

Study day is defined relative to the date of the first infusion (Week 1) in the current study. For assessments that occur after this visit date, study day is calculated as (assessment date – first infusion date + 1). For assessments that occur prior to first infusion date, study day will be calculated as (assessment date – first infusion date); there is no Study Day 0.

Treatment-emergent adverse event

An AE will be considered to be a treatment-emergent AE (TEAE) for the current study if the AE begins on or after parent study Week 13 visit (Week 13 Day 3 visit for study 004) through the 12-week post-treatment follow-up visit in the current study.

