9.6 Safety, Tolerability, and Immunogenicity Analyses

9.6.1 Adverse Events, Serious Adverse Events, and Deaths

Adverse events will be collected beginning at informed consent until the end of the study. See Section 6 for definition of TEAE. Adverse events will be coded using MedDRA to assign an SOC and PT to each adverse event and TEAEs will be summarized.

An overall summary of TEAEs including the following categories will be presented for the Safety analysis set by disease group:

- Number of TEAEs reported
- Number and percentage of patients reporting at least one TEAE
- Number and percentage of patients with at least one related TEAE (see definition in Section 6)
- Number and percentage of patients with at least one TEAE leading to study medication withdrawal
- Number and percentage of patients with at least one serious TEAE
- Number of patients with at least one TEAE with fatal outcome

The number and percentage of patients reporting TEAEs will also be summarized for the categories below. Counts will be by patient, not event, and patients will only be counted once within each SOC or PT. Tabulations will be sorted by descending frequency of the number of patients reporting the TEAE for each SOC and by PT within each SOC. Additionally, patients with multiple events within a particular SOC or PT will be counted under the category of their most severe event within an SOC or PT for summaries by maximum grade. Summaries to be provided are the following:

- TEAEs by MedDRA PT
- TEAEs by MedDRA SOC and PT

- Related TEAEs by MedDRA SOC and PT
- TEAEs by MedDRA SOC, PT, and maximum CTCAE grade
- SAEs by MedDRA SOC and PT
- TEAEs leading to study medication withdrawal by MedDRA SOC and PT
- TEAEs with a fatal outcome by MedDRA SOC and PT

TEAEs and non-TEAEs will be listed together.

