Preferred Term 3	xx (xx.x)	xx (xx.x)	xx (xx.x)	xx (xx.x)	xx (xx.x)	xx (xx.x)
Preferred Term 4	xx (xx.x)	xx (xx.x)	xx (xx.x)	xx (xx.x)	xx (xx.x)	xx (xx.x)
Preferred Term 5	xx (xx.x)	xx (xx.x)	xx (xx.x)	xx (xx.x)	xx (xx.x)	xx (xx.x)
...						
System Organ Class 3						
...						

Note: FSHD=Facioscapulohumeral muscular dystrophy; LGMD2B=Limb-girdle muscular dystrophy 2B; EO-FSHD=Early Onset Facioscapulohumeral muscular dystrophy

Note: Adverse events are coded using MedDRA version 18.1 and graded using CTCAE v4.03. For each system organ class and preferred term, patients are included only once at the maximum severity.

Note: Percentage based on the number of patients in the Safety population Cumulative.

Source: Listing xx.x.xx, Dataset: [NAME], Program: xxxxxx.sas, Output: T_14_2_1_4_XXXXX.rtf, Generated on: DDMMYYYY HH:MM

Page x of y

Programming Note: Repeat page for each disease group (FSHD, EO-FSHD, and LGMD2B) and total. Sort by decreasing frequency of "Total" column for both SOC and preferred term. Preferred terms appearing in any group should be displayed in all groups (i.e., keep 0 rows in other groups).

14.2.1.5 Treatment-Emergent Adverse Events Leading to Study Medication Withdrawal by System Organ Class and Preferred Term (Safety Population Cumulative)

Programming Note: Repeat previous table 14.2.1.2, subsetting for TEAEs with action taken of study drug withdrawn. Replace first row header with: "Any TEAE with action taken of study drug withdrawn."

14.2.1.6 Serious Treatment-Emergent Adverse Events by System Organ Class and Preferred Term (Safety Population Cumulative)

Programming Note: Repeat previous table 14.2.1.2, subsetting for serious TEAEs. Replace first row header with: "Any serious TEAE."

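### Both SAP tables that count serious events are limited to TEAEs, so a drug-related SAE starting after the 12-week visit would be listed but not tabulated

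*SAP*

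**What the plan says.** **Endpoint.** Protocol 3.2.1 gives the first safety endpoint as "Incidence of TEAEs and serious adverse events (SAEs) overall and by intensity". SAP 4.1.1 likewise lists TEAEs and SAEs as separate items.

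**Analysis in the protocol.** Section 9.2.9 says "Severe TEAEs, SAEs, and discontinuation rates of study therapy due to TEAEs also will be summarized", and later "Deaths, SAEs, and TEAEs resulting in study discontinuation will be tabulated, if warranted by the data". In the first sentence the treatment-emergent qualifier is attached to severe events and to discontinuations, but not to SAEs.

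**Collection.** Protocol 8.5.10.4 runs SAE collection from signing of the consent form "through the EOS visit, or after the end of the study if thought to be related to ATYR1940". Section 8.5.10.2 has a similar extension for AEs thought related to study drug, although its window opens at the first dose in this study.

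**Analysis in the SAP.** Section 9.6.1 promises a summary of "SAEs by MedDRA SOC and PT". The shell that delivers it is Table 14.2.1.6, with the note "Repeat previous table 14.2.1.2, subsetting for serious TEAEs". The overview, Table 14.2.1.1, has a row for patients with any serious TEAE. SAP 6.0 lets a TEAE begin "through the 12-week post-treatment follow-up visit in the current study" at the latest, and protocol 6.2 states: "The 12-week follow-up visit is the End-of-Study (EOS) visit".

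**The concern.** The protocol collects one kind of event after the end of the study: events thought to be drug-related. The SAP's serious-event tables exclude exactly that kind when the event is serious and starts after the 12-week visit. Any omission runs in one direction, because removing related serious events can only lower the reported SAE incidence.

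Long-term safety, tolerability and immunogenicity form the first study objective. A reader of the clinical study report will probably take the serious-event tables as the answer to the SAE endpoint. If those tables hold a narrower set than the protocol names, the report should say so. At present neither the SAP's list of changes from the protocol nor the table footnotes do.

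**Working it through.** The documents give no event rate, power or sample size calculation for this point, so the check is mainly a comparison of windows.

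**Step 1: where each window closes**

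| Item | Source | Closes at |
|---|---|---|
| SAE collection, any cause | Protocol 8.5.10.4 | EOS visit |
| SAE collection, thought drug-related | Protocol 8.5.10.4 | No fixed end |
| TEAE, SAP | SAP 6.0 | 12-week follow-up visit (= EOS, protocol 6.2) |
| TEAE, protocol | Protocol 9.2.9 | 12-week follow-up visit |
| Tables 14.2.1.1 (serious row) and 14.2.1.6 | SAP Appendix 5 | As for TEAE |

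The any-cause SAE window and the TEAE window close at the same visit. The gap is therefore limited to drug-related SAEs starting after it. The protocol's own TEAE definition also closes at this visit, so the gap comes from limiting the SAE tables to TEAEs and not from the closing date itself.

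**Step 2: follow each kind of event through the SAP**

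- SAE starting on treatment or by the 12-week visit: it is a TEAE and is counted in both tables.
- SAE starting after the 12-week visit and not thought related: the protocol does not ask for it, so nothing conflicts.
- SAE starting after the 12-week visit and thought related: the protocol asks for it, but it is not a TEAE. It is absent from 14.2.1.1, 14.2.1.6 and the related-TEAE table 14.2.1.3. If fatal, it also misses the fatal-outcome row of 14.2.1.1, which has the same limit. If it is in the database it appears in Listing 16.2.9, which takes all AEs whatever their TEAE status.
- Drug-related SAE in a patient who leaves early: SAP 8.1 writes early termination as an alternative beside each follow-up visit, and protocol 6.4.2 places the termination assessments within 7 days of the last dose where feasible. If SAP 8.1 is read as closing the TEAE window at that visit, it closes about 84 − 7 = 77 days or more before the scheduled 12-week visit, and later events fall outside. If SAP 8.1 is not read that way, the SAP gives this patient no closing date.

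**Step 3: is the narrowing declared?** SAP 1.1 records the change of baseline, several schedule clarifications and the age range. It does not mention limiting SAEs to serious TEAEs.

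**Step 4: size.** Protocol 9.1 expects up to 24 patients.

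- One patient omitted: 1/24 = 4.2 percentage points.
- Range under an assumed zero to three patients: 0/24 = 0 to 3/24 = 12.5 points.

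These shifts apply to the row for any serious event only if the patient has no other serious TEAE; otherwise that row is unchanged and only the SOC and preferred-term rows can be affected. With fewer than 24 patients, and in the disease-group columns, each patient weighs more.

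**The case against.** The case for leaving the tables alone is substantial.

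- **A fixed window is a legitimate choice.** Reports after EOS arrive without scheduled ascertainment, so mixing them into an incidence table blurs what the rate means. This stands, and it is why the late events need their own line.
- **The protocol never says that the endpoint counts post-EOS SAEs.** A reader might infer that it does from the collection rule. But 3.2.1 gives no window, 8.5.10.4 is a reporting section, and 9.2.9 describes its AE incidence summary in terms of events during the study. The inference is not supported. What the text does support is that SAEs are named apart from TEAEs.
- **SAP 9.6.1 can be read as agreeing with the shell.** Its SAE item sits under a sentence introducing summaries of patients with TEAEs. The difference is one of label, and it would be too strong to say that the documents define the SAE endpoint in three ways. Seriousness is defined once, in protocol 8.5.10.1.3; what differs is the set summarized.
- **Late events are not lost.** Listing 16.2.9 shows seriousness, relationship and TEAE status, and with at most 24 patients a late SAE would be easy to see. This stands, but a listing does not give an incidence, which is the stated endpoint.
- **There may be no such events.** Protocol 2.3 gives a half-life of about 3 to 6 hours, so 84 days (84 × 24 = 2,016 hours) is 2,016/6 = 336 to 2,016/3 = 672 half-lives. That does not rule out late immune events: protocol 8.5.9.3 itself continues ADA testing after the 12-week visit when levels are elevated. No rate is documented either way.
- **The data may not be there.** Protocol 8.5.10.3 requires eCRF recording only up to EOS, so a later SAE might not reach the analysis database. This stands and limits the fix to what is recorded.

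Two further inferences should be avoided. A TEAE window with no closing date for a patient without a 12-week visit does not by itself understate rates, since an open window excludes nothing. And the instruction in protocol 8.5.9.4 to watch for late sequelae concerns patients with generalized infusion reactions; it is not a general rule for SAE analysis.

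**Conclusion.** The point holds as a mismatch between an endpoint named as SAEs and tables limited to serious TEAEs, with a narrow practical consequence. A drug-related SAE starting after the 12-week visit would reach Listing 16.2.9 but no incidence table. The same applies after an early-termination visit, if SAP 8.1 is taken to close the window there. The effect on the any-SAE rate is nil if there are no such events and 4.2 percentage points per newly omitted patient at 24 patients. The zero-to-three scenario is only an illustration of scale.

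The conclusion assumes that the shells are programmed as written and that the late event is recorded in the study database. It does not depend on the protocol having intended post-EOS SAEs to count in the endpoint; the undeclared difference between SAEs and serious TEAEs is enough. It is a cheap improvement, not a flaw that threatens the study's conclusions.

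**What to change.** - In Table 14.2.1.6 and the serious row of Table 14.2.1.1, count all SAEs recorded in the study database, split by TEAE yes/no.
- Add a separate line for drug-related SAEs (possibly, likely or definitely, as in SAP 6.0) starting after the 12-week or early-termination visit.
- Make the SAE label in SAP 9.6.1 and the title of Table 14.2.1.6 say the same thing.
- If the sponsor prefers to keep the tables to serious TEAEs, state this in SAP 1.1 and say that later SAEs are listed only. That removes the undeclared difference but still leaves late events without an incidence.

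The cost is SAP wording and two shell edits. No additional data collection is needed for SAEs already in the database. The small downside is a possibly higher reported SAE rate that includes events without scheduled ascertainment; the separate line lets the reader see that part and set it aside. No new calendar cut-off for the TEAE window is needed.

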14.2.1.7 Treatment-Emergent Adverse Events by Preferred Term (Safety Population Cumulative)

	EO-FSHD (N = XX) n (%)	FSHD (N = XX) n (%)	LGMD2B (N = XX) n (%)	Total (N = XX) n (%)
Parent and Current Studies Overall				
Any treatment-emergent adverse event	xx (xx.x)	xx (xx.x)	xx (xx.x)	xx (xx.x)
Preferred Term 1	xx (xx.x)	xx (xx.x)	xx (xx.x)	xx (xx.x)
Preferred Term 2	xx (xx.x)	xx (xx.x)	xx (xx.x)	xx (xx.x)
Preferred Term 3	xx (xx.x)	xx (xx.x)	xx (xx.x)	xx (xx.x)
Preferred Term 4	xx (xx.x)	xx (xx.x)	xx (xx.x)	xx (xx.x)
Preferred Term 5	xx (xx.x)	xx (xx.x)	xx (xx.x)	xx (xx.x)
...				
Current Study (ATYR1940-C-006) Overall				
Any treatment-emergent adverse event	xx (xx.x)	xx (xx.x)	xx (xx.x)	xx (xx.x)
Preferred Term 1	xx (xx.x)	xx (xx.x)	xx (xx.x)	xx (xx.x)
Preferred Term 2	xx (xx.x)	xx (xx.x)	xx (xx.x)	xx (xx.x)
Preferred Term 3	xx (xx.x)	xx (xx.x)	xx (xx.x)	xx (xx.x)
Preferred Term 4	xx (xx.x)	xx (xx.x)	xx (xx.x)	xx (xx.x)
Preferred Term 5	xx (xx.x)	xx (xx.x)	xx (xx.x)	xx (xx.x)
...				

Note: FSHD=Facioscapulohumeral muscular dystrophy; LGMD2B=Limb-girdle muscular dystrophy 2B; EO-FSHD=Early Onset Facioscapulohumeral muscular dystrophy

Note: Adverse events are coded using MedDRA version 18.1. Only treatment-emergent adverse events are summarized. For each system organ class and preferred term, patients are included only once.

Note: Percentage based on the number of patients in the Safety population cumulative.

Source: Listing xx.x.xx, Dataset: [NAME], Program: xxxxxx.sas, Output: T_14_2_1_7_XXXXX.rtf, Generated on: DDMMYYYY HH:MM

Page x of y

14.2.2 LABORATORY DATA TABLES

14.2.2.1.1 Hematology Results by Visit (Safety Population Cumulative)

Disease Study Visit	Parameter = Parameter 1 (units, if applicable)					
	Actual			Change from Baseline		
	N	Mean (SD)	Median (Min, Max)	N	Mean (SD)	Median (Min, Max)
Total (N = xx)						
Parent Study						
Baseline	xx	xx.x (xx.xx)	xx.x (xx, xx)			
Week 14/1-Week Follow-up	xx	xx.x (xx.xx)	xx.x (xx, xx)	xx	xx.x (xx.xx)	xx.x (xx, xx)
Current Study (ATYR1940-C-006)						
Week 1	xx	xx.x (xx.xx)	xx.x (xx, xx)	xx	xx.x (xx.xx)	xx.x (xx, xx)
Week 4	xx	xx.x (xx.xx)	xx.x (xx, xx)	xx	xx.x (xx.xx)	xx.x (xx, xx)
Week 8	xx	xx.x (xx.xx)	xx.x (xx, xx)	xx	xx.x (xx.xx)	xx.x (xx, xx)
...						
1-Week Post-treatment Follow-up	xx	xx.x (xx.xx)	xx.x (xx, xx)	xx	xx.x (xx.xx)	xx.x (xx, xx)
4-Week Post-treatment Follow-up	xx	xx.x (xx.xx)	xx.x (xx, xx)	xx	xx.x (xx.xx)	xx.x (xx, xx)
12-Week Post-treatment Follow-up	xx	xx.x (xx.xx)	xx.x (xx, xx)	xx	xx.x (xx.xx)	xx.x (xx, xx)
...						
<repeat for>						
EO-FSHD (N = xx)						
FSHD (N = xx)						
LGMD2B (N = xx)						

Note: FSHD=Facioscapulohumeral muscular dystrophy; LGMD2B=Limb-girdle muscular dystrophy 2B; EO-FSHD=Early Onset Facioscapulohumeral muscular dystrophy

Note: Baseline is defined as the baseline in the parent study.

Source: Listing xx.x.xx, Dataset: [NAME], Program: xxxxxx.sas, Output: T_14_2_2_1_1_XXXXX.rtf, Generated on: DDMMYYYY HH:MM

Page x of y

Programming Note: Baseline will be the last value prior to 1st ATYR1940 dose at Week 2 in the parent study. Labs collected due to the result of an IRR will not be summarized, but will be provided in the data listing. Parameters are listed in Section 9.6.2 of SAP text. Parameters should be presented in the same order as the protocol.

14.2.2.1.2 Shift Summary of Hematology Results by Reference Range and Visit (Safety Population Cumulative)

Parameter Study Visit Baseline Value	EO-FSHD (N = XX)				
	Post Baseline Value				
	Low	Normal	High	Total	Missing
Laboratory parameter 1					
Parent Study					
Week 14/1-Week Follow-up					
Low	xx (xx.x)	xx (xx.x)	xx (xx.x)	xx	xx
Normal	xx (xx.x)	xx (xx.x)	xx (xx.x)	xx	xx
High	xx (xx.x)	xx (xx.x)	xx (xx.x)	xx	xx
Total	xx (xx.x)	xx (xx.x)	xx (xx.x)	xx	xx
Missing	xx	xx	xx	xx	xx
Current Study (ATYR1940-C-006)					
Week 1					
Low	xx (xx.x)	xx (xx.x)	xx (xx.x)	xx	xx
Normal	xx (xx.x)	xx (xx.x)	xx (xx.x)	xx	xx
High	xx (xx.x)	xx (xx.x)	xx (xx.x)	xx	xx
Total	xx (xx.x)	xx (xx.x)	xx (xx.x)	xx	xx
Missing	xx	xx	xx	xx	xx
Week 4					
Low	xx (xx.x)	xx (xx.x)	xx (xx.x)	xx	xx
Normal	xx (xx.x)	xx (xx.x)	xx (xx.x)	xx	xx
High	xx (xx.x)	xx (xx.x)	xx (xx.x)	xx	xx
Total	xx (xx.x)	xx (xx.x)	xx (xx.x)	xx	xx
Missing	xx	xx	xx	xx	xx

...
 Note: FSHD=Facioscapulohumeral muscular dystrophy; LGMD2B=Limb-girdle muscular dystrophy 2B; EO-FSHD=Early Onset Facioscapulohumeral muscular dystrophy
 Note: Baseline is defined as the baseline in the parent study.
 Note: Total column is the number of patients with at least one post baseline result.
 Note: Percentages are based on the total number of patients with both a baseline and a post baseline result at that visit.
 Source: Listing xx.x.xx, Dataset: [NAME], Program: xxxxxx.sas, Output: T_14_2_2_1_2_XXXXX.rtf, Generated on: DDMMYYYY HH:MM
 Page x of y

Programming Note: Repeat page for each disease type (FSHD, EO-FSHD, and LGMD2B) and total. Repeat for each visit. Continue for all hematology parameters listed in SAP text. Baseline will be the last value prior to 1st ATYR1940 dose at Week 2 in the parent study. Parameters should be presented in the same order as the protocol. Labs collected due to the result of an IRR will not be summarized, but will be provided in the data listing.

